6. STUDY OBJECTIVES

The primary purpose of the study is to assess the change in serum 25-OH vitamin D concentrations following 3 doses of 300,000 IU of a novel vitamin D3 gel. The secondary objective is to assess the safety (based on any skin rash or other skin reactions, as well as calcium and parathyroid hormone levels) following treatment.

.

7. INVESTIGATIONAL PLAN

7.1 Overall Study Design

20 healthy adults with known vitamin D deficiency (defined as serum 25-OH vitamin D concentration < 20 ng/ml) will receive 3 doses of 300,000 IU of topical vitamin D once per week for three weeks. Each dose will be made up of two applications of 150,000 IU cholecalciferol in .75 ml of gel applied consecutively to the upper arms (one 150,000 IU application per arm).

Blood will be drawn at baseline prior to the first dose (Day 0) and on Days 7, 14, and 21. Total serum 25-OH vitamin D will be assayed at each draw. Parathyroid hormone level will be assayed at baseline and on day 21.

7.2 Study Duration

The maximum duration of treatment is 14 days (study Days 0, 7 and 14). Subjects will be followed for change in vitamin D blood level and for safety until Study Day 21. It is anticipated that the study will last 4 months to enroll and complete dosing and assessment of 20 patients.

8. STUDY POPULATION

8.1 Inclusion Criteria

A subject must meet all of the following inclusion criteria to be eligible for enrollment in this study:

1. Known vitamin D deficiency based on blood work obtained prior to study consent defined as serum 25-hydroxyvitamin D less than or equal to 20 ng/mL within 30 days prior to study entry.
2. Adult, age 18 to 85 years, male or female
3. If on oral vitamin D therapy, have been on a stable dose for the previous 90 days.

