Of all of the forms of vitamin D, cholecalciferol (Vitamin D3) has been viewed as having the best overall combination of safety and efficacy, assuming normal kidney and liver function. In the US, cholecalciferol has primarily been available as an oral supplement at fairly low doses (most commonly 1000 – 2000 IU). In otherwise healthy patients, a common US standard of care for treatment of low serum vitamin D is to give 50,000 IU Vitamin D orally per week for four weeks (total dose 200,000 IU) until levels are brought up into the adequate

[figure not shown]

Figure 1. Absorption kinetics of oral Vitamin D3.

effective long term treatment of vitamin D deficiency. The proposed study aims to investigate both safety and efficacy of a topically applied vitamin D that is likely to be more effective, convenient, or acceptable for many individuals.

A wide variety of dosing schedules for Vitamin D have been documented¹⁸. Recently Vieth's team conducted a study with oral cholecalciferol in 48 elderly women (81 ± 8 years)¹⁹. The study tested oral cholecalciferol (D3) up to 45,000 IU once every 28 days. The study showed that a single oral dose of 45,000 IU dissolved in alcohol generally produced a rise in serum vitamin D of about 10 ng/ml. A second oral dose 28 days later further increased the serum vitamin D level by about another 10 ng/ml. Thus, the total increase after two oral doses (90,000 IU) was about 20 ng/ml. Although following oral dosing, rises in serum Vit D can be seen up to one month following administration, Vieth's study demonstrated that most of the rise (>60%) in Vitamin D occurs within 7 days. (Figure 1). No one receiving oral monthly dosing of 45,000 IU Vitamin D3 developed hypercalcemia.

Vitamin D Product Development

Innovative Pharmacy Services, Inc. has developed a vitamin D3 topical gel using ingredients that are identified in the USP/NF and/or designated in the list of Inactive Ingredients in FDA Approved Drugs. The ingredients in the topical gel are well known in the industry and have references in the pharmaceutical literature and some have available FDA drug master file information. A single applicator contains 0.75 g of gel, containing 150,000 international units of vitamin D3 (cholecalciferol). One dose will consist of two applicators. One applicator will be applied to each of the subject's upper arm for a total dose of 300,000 units.

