In the process of normal physiologic production, previtamin D3 can isomerize in a reversible reaction to form the photoproducts, tachysterol-3 or lumisterol-3. These isomers do not enhance intestinal calcium absorption and do not significantly enter the circulation. The inactive metabolic products are sloughed off when skin cells are naturally shed. Removal of previtamin D3 provides a mechanism to prevent vitamin D toxicity from prolonged sun

exposure²⁵, and may further increase the potential safety of topical Vitamin D3 administration. The Mayo Clinic reports that Vitamin D is 'likely' safe when applied to the skin¹².

The effectiveness of topical absorption for the proposed product is unknown, however topical absorption is substantially less effective than the intramuscular injection of Vitamin D3. In the first three candidates, 300,000 units applied over three weeks resulted in an insignificant average change in Vitamin D level, as follows.

Baseline	Week 1	Week 2	Week 3	change
10.2	9.4	10.4	12.1	1.2

Oral administration of 50,000 IU should produce a 10 ng/ml increase in total serum Vitamin D¹³. The topical application of 300,000 IU, therefore, was substantially less effective than one 50,000 IU oral dose. . The study will use three doses of 300,000 IU applied one week apart with safety and outcome measures after each. This is hoped to provide a greater difference in vitamin D level than that seen in one oral 50,000IU supplement, but should produce less change than the typical US replacement dosing of three oral supplements, If the change in total serum Vitamin D level after the topical application of 900,000 IU in the first 10 subjects is consistently less than 10 mg/ml then the study will be discontinued.

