9. TREATMENT OF SUBJECTS

9.1 Treatment Assignment

This is an open-label, nonrandomized study in which all subjects will receive topical vitamin D gel.

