We will initially administer 100,000 units topically to subjects, and check serum Vitamin D and calcium levels one week later. Dosing will be discontinued if a patient achieves a Vitamin D level of greater than normal (> 90 ng/ml) or if serum calcium rises above normal (> 10.2 mg/dl). Additional doses of 100,000 units will be administered on days 7 and 14. The outcome of interest will be the effect on total serum Vitamin D at 21 days. Although a change in calcium is unlikely, calcium will be monitored for safety.

Vitamin D may alter glucose values and improve glucose control in individuals with diabetes²⁶. Although individuals with diabetes will not be excluded, we will instruct any subjects with diabetes to more closely monitor glucose values during the course of the study.

Parathyroid hormone will be measured at baseline and on Day 21 to determine if vitamin D correction changes the level of this metabolic calcium regulatory hormone.

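### The stable-dose criterion covers only current oral vitamin D users, so treatment recently stopped or given by another route can leave Day 0 as a moving baseline

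*Protocol*

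**What the plan says.** Protocol 8.1 sets three inclusion criteria, and the Synopsis repeats them. Criterion 3 reads: "If on oral vitamin D therapy, have been on a stable dose for the previous 90 days". It is the only eligibility rule about other vitamin D treatment. The ten exclusions in 8.2 contain no washout and do not mention vitamin D that was recently stopped, injected or given by any other non-oral route. The Day 0 procedures in 11.1.1 do not include a history of earlier vitamin D treatment.

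Criterion 1 requires "serum 25-hydroxyvitamin D less than or equal to 20 ng/mL within 30 days prior to study entry". A fresh level is drawn on Day 0, but no section makes that result a condition of eligibility.

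On design, Protocol 9.1 states: "This is an open-label, nonrandomized study in which all subjects will receive topical vitamin D gel". On the outcome, 13.1.1 states: "The outcome of interest will be the effect on total serum Vitamin D at 21 days". Neither Protocol section 14 nor the SAP plans an adjustment or sensitivity analysis for prior vitamin D.

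On the time course of an oral dose, Protocol 5.1 says that "rises in serum Vit D can be seen up to one month following administration" and that "most of the rise (>60%) in Vitamin D occurs within 7 days". It also describes four weekly oral doses of 50,000 IU as common US care for a low level, with daily maintenance afterwards. On the size of the response, 5.2.2 states: "Oral administration of 50,000 IU should produce a 10 ng/ml increase in total serum Vitamin D".

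**The concern.** Criterion 3 is conditional: it applies only to someone who is on oral therapy at entry. A person who has finished or stopped is arguably not on therapy, so the condition is never reached. A person treated by injection falls outside the word oral. The 90-day clause shows that the sponsor wants a steady background intake; the wording misses those who have just stopped.

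Candidates are found by chart review for known deficiency, a finding that by the protocol's own account is often treated. Because the qualifying test may be 30 days old, there is room for treatment between that test and Day 0.

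With no control group, the change from Day 0 to Day 21 is the whole answer. If a subject's level is still climbing from earlier doses, the rise is added to the apparent gel effect. If it is falling from a raised level, the fall is subtracted. Such a subject may also no longer be deficient when the gel is applied, although Protocol 7.1 describes a deficient population.

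The point is about wording on treatment before entry. It does not concern vitamin D taken during Days 0 to 21.

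**Working it through.** **1. The plan's own sample size.** Protocol 14.4 and SAP 1.4 can be checked with a two-sided paired t test at alpha 0.05 (sidedness is not stated; two-sided is assumed).
- SD of the difference 5.6, effect 6.4, n = 10: power 89.4%, against the stated 90%.
- SDs 4 and 12, assuming zero correlation: SD of the difference = √(16 + 144) = 12.65. With effect 10 and n = 20, power is 91.8%.

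Both reproduce to a fair approximation. The present issue is bias, not precision, so closing the gap leaves the 20 subjects unchanged.

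**2. Does a course fit before Day 0?** Take study entry as Day 0. Four weekly doses at Days -28, -21, -14 and -7 fit between a qualifying test at Day -30 to Day -28 and Day 0.

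**3. Inputs for the rise still to come.**
- 10 ng/ml per oral 50,000 IU (Protocol 5.2.2).
- More than 60% of the rise by 7 days, and further rise possible for up to a month (Protocol 5.1).
- Assumptions, not in the documents: the rest arrives linearly from day 7 to day 28; nothing is eliminated; more than 60% is taken first as exactly 60%, then as 80%.

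**4. Fraction of a dose's rise still to come.** For a dose given d days before Day 0, with 7 ≤ d ≤ 28 and a share p risen by day 7:

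remaining = (1 − p) × (28 − d) / 21

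| Dose day | p = 60% | p = 80% |
|---|---|---|
| -28 | 0 | 0 |
| -21 | 0.133 | 0.067 |
| -14 | 0.267 | 0.133 |
| -7 | 0.400 | 0.200 |
| Sum | 0.80 | 0.40 |
| × 10 ng/ml | 8.0 | 4.0 |

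The Day -7 dose reaches 28 days on Day 21, so all of this remainder falls inside the outcome window. It is 40% to 80% of the 10 µg/L that Protocol 14.4 calls clinically relevant (1 µg/L = 1 ng/ml).

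**5. The opposite direction.** Four doses give 4 × 10 = 40 ng/ml in all. At p = 60%, 40 − 8 = 32 has already risen by Day 0; at p = 80%, 40 − 4 = 36. A fall in that part of 8/32 = 25% over 21 days, or 4/36 = 11%, would cancel the remaining rise; a larger fall would turn the drift negative. The documents give no elimination rate, so the sign is not settled.

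**6. Effect on the mean.** If k of 20 subjects are affected, the shift is at most k × 4/20 to k × 8/20: 0.2 to 0.4 ng/ml for k = 1, 0.8 to 1.6 for k = 4, and 2.0 to 4.0 for k = 10. The documents give no basis for choosing k.

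**The case against.** The strongest reply is that the route in is narrow.

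- **The entry test blocks many.** A person whose level had been raised above 20 ng/mL before the test fails criterion 1. This stands. It leaves mainly treatment given between the test and Day 0, or too shortly before the test to have raised it.
- **The protocol's own care pathway is largely caught.** Section 5.1 has the weekly course followed by daily supplements. A patient who moved on to maintenance is on oral therapy with a recent change and is already excluded. This stands. A subject whose last weekly dose was seven days ago might also be read as still on therapy, but the protocol does not define the term.
- **The Day 0 sample is a fresh baseline.** It absorbs every rise before Day 0, so only later movement matters. A Day 0 value some 32 ng/ml above the untreated level would also be conspicuous. True, but nothing in the plan says what to do on seeing one.
- **This is a small proof of concept.** Protocol section 14 and the SAP call the analysis descriptive, although the Synopsis names a paired t test. A drift in the mean change is present under either.

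Some stronger readings are tempting. A reader might infer that prior treatment must flatter the gel; step 5 shows that the direction depends on timing and on an elimination rate that the documents do not give. A reader might infer that one such subject could defeat the rule for stopping after the first 10. For the course ending on Day -7, 8 ng/ml alone is below 10. The same model gives about 15.4 for a course ending on Day -1, but that ignores elimination, and someone dosed the day before is more readily judged to be on therapy. A reader might treat injections as an equal risk; 5.2.2 describes them as French practice, and there is no time course and no sign of use at this Minnesota centre. The pilot row in 5.2.2 is not a safe yardstick either: 12.1 − 10.2 = 1.9, while the printed change is 1.2, and the total dose was lower.

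**Conclusion.** The gap is real in the wording of both the Synopsis and 8.1, and nothing else in the protocol or SAP closes it. For an affected subject, the Day 0 to Day 21 change mixes the gel effect with the course of earlier treatment, in a direction that cannot be known in advance.

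The upward drift is at most about 4 to 8 ng/ml for a four-week oral course ending on Day -7. That rests on a linear remainder, no elimination, and 60% to 80% of the rise by day 7. It is an upper bound for that schedule, not an expected bias. The number of subjects it could touch is unknown, and nothing can be computed for injected vitamin D. The documents do not support a claim that the trial's result will be materially distorted. They support a cheap improvement to one criterion.

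**What to change.** Reword criterion 3 in Protocol 8.1 and in the Synopsis to: *No start, stop or dose change of vitamin D therapy, by any route, in the 90 days before Day 0.* Non-users and stable users both remain eligible. The look-back is the one that the protocol already uses, now applied to people who stopped as well as to those who changed dose. Ninety days is longer than the one-month rise in 5.1; since the documents give no rate of decline after a load, the sponsor should state its reason for the period it keeps.

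The cost is one sentence in two places, one added chart-review question about the last vitamin D treatment and its route, and the loss of some recently treated candidates. How many cannot be judged from the documents. The sample size does not change.

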8.2 Exclusion Criteria

Subjects are excluded from this study if any of the following conditions are met:

1. History of acute or chronic liver disease with elevated liver function tests, chronic kidney disease (stage 3 or greater, eGFR <60), uncontrolled thyroid disease (elevated thyroid function tests), primary or secondary hyperparathyroidism, hypercalcemia, or multiple endocrine neoplasia.
2. Hypercalcemia defined as elevated corrected serum calcium (>10.2 mg/dl) measured within 3 months prior to study.
3. eGFR <60 mL/min within 3 months prior to study.
4. Active cancers
5. Women who are pregnant or breastfeeding
6. Individuals who are unable to give informed consent
7. Individuals with psoriasis, active eczema or other active skin disease, or who are currently receiving treatments or medications to control skin disease
8. Individuals who do not agree to refrain from using tanning beds for the duration of the study.
9. Individuals who do not agree to avoid submerging the gel site in water for 8 hours after gel application.
10. Family members of the study faculty or staff.

8.3 Criteria for Withdrawal

A subject has the right to withdraw fully or partially from the study at any time and for any reason without prejudice to his or her future medical care by the physician or at the institution.

Withdrawal of full consent for a study means that the subject does not wish to receive further investigational treatment and does not wish to or is unable to continue further in study participation. Subject data up to withdrawal of consent will be included in the analysis of the

study. The Investigator will discuss with the subject appropriate procedures for withdrawal from the study. Withdrawal of partial consent from a study means that the subject does not wish to take investigational product or other protocol-required therapy any longer but is still willing to collaborate in providing further data by continuing on study. Should a subject request or decide to withdraw from the study, all efforts will be made to complete and report the observations as thoroughly as possible up to the date of withdrawal. All information should be reported on the applicable case report form (CRF). Reasons for removal from protocol-required treatment or observation might include:

- partial/full withdrawal of consent
- administrative decision by the Sponsor-Investigator
- pregnancy
- ineligibility
- significant protocol deviation
- subject noncompliance
- adverse event, including rash or other skin reaction
- Death

8.4 Replacement of Subjects

Subjects who withdraw or are removed from the study prior having their Day 7 blood draw for a reason other than a drug-related adverse event will be replaced.

9. TREATMENT OF SUBJECTS

9.1 Treatment Assignment

This is an open-label, nonrandomized study in which all subjects will receive topical vitamin D gel.

9.2 Treatment Administration

Subjects will be provided with written and verbal instructions about Vitamin D deficiency during their baseline/Day 1 visit. A study nurse or physician will supervise each treatment application to ensure that the gel is applied correctly. Prior to application of the gel, 2 strips of paper tape will be applied to the subject's upper arms. One strip will be applied approximately 2 inches below the subject's shoulder and the second strip will be applied approximately 2 inches above the subject's elbow. The entire contents of one syringe (0.75 mL of gel) will be applied onto their arm in a straight line, from approximately 1 inch below the first strip of paper tape to approximately 1 inch above the second strip of paper tape. The subject will be instructed to gently rub the gel into their upper arm with their fingertips, while staying between the two pieces of paper tape, for approximately 2 minutes or until the gel has been absorbed. After completing the application process on both arms, the subject will wash his/her hands thoroughly.

A complete description of the administration process can be found in Appendix 1.

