
No. Subjects:	20 subjects will participate. If the change from baseline in 25-OH vitamin D is consistently less than 10 µg/L in the first 10 subjects then the study will be discontinued.
No. Centers:	The study will be conducted at the University of Minnesota (single center)
Study Duration:	The maximum duration of treatment is 14 days (study Days 0, 7 and 14). Subjects will be followed for change in vitamin D blood level and for safety until Study Day 21. It is anticipated that the study will last 4 months to enroll and complete dosing and assessment of 20 patients.
Objectives of the Study:	The primary objective of the study is to determine the change in vitamin D blood levels following 3 doses of topical vitamin D ₃ treatment. The secondary objective is to assess the safety (based on skin rash and/or other reaction, as well as calcium and parathyroid hormone levels) following the application of 3 doses of vitamin D ₃ gel.
Study Endpoints: (Primary and Secondary)	The primary endpoint is to establish the average change in vitamin D blood levels following 3 doses of treatment with vitamin D gel. The secondary study endpoint is the number of subjects who have any skin rash and/or other skin reaction following treatment with the vitamin D gel.
Study Design:	The study is a pre vs. post open-label trial to assess the change in vitamin D blood levels following treatment with 3 doses of topical vitamin D gel. Subjects with known vitamin D deficiency will be consented and enrolled. They will have a blood draw prior to dosing on Day 0 (to obtain a baseline vitamin D level) and will receive topical vitamin D ₃ on Days 0, 7 and 14. On Days 7, 14, and 21 subjects will return to the clinic for a post-dose blood draw and to be assessed for any signs of skin rash and/or reaction. If a subject has a skin rash and/or reaction at any time during the study, he/she should return to the clinic for assessment as soon as possible. Any rash and/or skin reaction will be photographed and diagnosed.
Eligibility Criteria (Inclusion and Exclusion):	
Inclusion criteria:
 
 Known vitamin D deficiency based on blood work obtained prior to study consent defined as serum 25-hydroxyvitamin D less than or equal to 20 ng/mL within 30 days prior to study entry. (Normal \geq to 30 µg/L total 25-OH Vitamin D) Adult, age 18 to 85 years, male or female If on oral vitamin D therapy, have been on a stable dose for the previous 90 days.

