5. INTRODUCTION

5.1 Vitamin D Deficiency

Vitamin D insufficiency is an emerging and compelling public health issue. Recent studies suggest that 19% of the U.S. population is at risk for vitamin D inadequacy¹, although this may underestimate the number of people at risk from suboptimal vitamin D levels². More than 40% of U.S. and European elderly men and women living in the community are deficient in Vitamin D³, and more than 50% of postmenopausal women taking medication for osteoporosis⁴. Diverse population subgroups are deficient in Vitamin D including Arab women and lactose intolerant individuals who consume less vitamin D from fortified products⁵. In a Boston hospital, 25% of healthy students, physicians, and residents were found to be vitamin D-deficient, despite drinking a glass of milk and taking a multivitamin daily and eating salmon at least once a week⁶. By the end of the winter, it has been estimated that 42% of 15- to 49-year-old black females throughout the United States have 25-hydroxyvitamin D levels below 20 ng per milliliter. The implications of this are far-reaching. In addition to well-known impacts on bone health, vitamin D status is thought to potentially influence a number of common diseases, including cancers, autoimmune disorders, and cardiovascular disease. Vitamin D deficiency may increase the risk of injury from falls as people age⁷, while early in life Vitamin D deficiency has been associated with increased risk of Type 1 diabetes^{8,9}. Other patient populations at increased risk for vitamin D insufficiency include individuals with fat malabsorption, chronic kidney disease, or obesity^{10,11,12}.

The Endocrine Society defines vitamin D deficiency as a 25(OH)D of 20 ng/ml (50 nmol/liter) or below, and vitamin D insufficiency as a 25(OH)D of 21–29 ng/ml (525–725 nmol/liter)¹³. They recommend measuring vitamin D using the serum circulating 25-hydroxyvitamin D (25(OH)D). The Institute of Medicine reports that persons are potentially at risk for inadequacy at serum 25OHD levels between 12 and 20 ng/mL (30 and 50 nmol/L)¹⁴. In sun-rich environments, normal levels have been estimated to be 54-90 ng/ml¹⁵. Although it is not known what the safe upper value for 25(OH)D is for avoiding hypercalcemia, most studies in children and adults have suggested that the blood levels need to be above 150 ng/ml before any concern arises¹⁶.

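### Deficiency instruction is given at the baseline visit of an uncontrolled pre-post study that neither limits nor records diet or supplement changes, so any intake it prompts would count as gel effect.

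*Protocol*

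**What the plan says.** Protocol section 9.2 (Treatment Administration): "Subjects will be provided with written and verbal instructions about Vitamin D deficiency during their baseline/Day 1 visit". The content of these instructions is not described, and they appear neither in Table 1 nor in the Day 0 procedure lists of the synopsis and section 11.1.1.

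Section 9.2 labels the visit Day 1 and the schedule labels it Day 0, but both mean the baseline visit. Section 7.1 puts the baseline sample there: "Blood will be drawn at baseline prior to the first dose (Day 0) and on Days 7, 14, and 21". The first gel application is at the same visit.

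On the comparison, the synopsis says: "The study is a pre vs. post open-label trial to assess the change in vitamin D blood levels". Section 9.1 confirms that there is no control: "This is an open-label, nonrandomized study in which all subjects will receive topical vitamin D gel". The primary endpoint in protocol section 14.2 and SAP section 1.2 is the change in vitamin D blood level after three doses.

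On other sources of vitamin D, inclusion criterion 3 in section 8.1 reads: "If on oral vitamin D therapy, have been on a stable dose for the previous 90 days". During the study the plan controls ultraviolet exposure. Section 8.2 excludes "Individuals who do not agree to refrain from using tanning beds for the duration of the study", and section 5.2.1 asks subjects to cover the upper arms outdoors in daylight. There is no corresponding on-study rule for diet or supplements. No visit records intake, and no analysis section mentions it. Section 15.6 says that the letter to the primary care physician will mention concomitant drugs to avoid, but it names none.

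**The concern.** The instruction and the gel start together in every subject. In a within-subject comparison without a control group, whatever follows the instruction is added to whatever follows the gel, and the data cannot separate them. Subjects told about their deficiency might start or increase a supplement or eat more fortified food. Section 5.1 treats such food as a source, noting that lactose-intolerant people "consume less vitamin D from fortified products".

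The assay does not rescue the comparison. Section 12.1 measures D2 and D3 separately, but section 5.1 describes the common US supplement as cholecalciferol, which is the form in the gel.

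At stake is the primary estimate and its attribution to absorption through the skin. The eligibility criterion does not help, because it looks back 90 days and applies only to people already on oral therapy. Intake is not recorded, so the problem could not be corrected at analysis.

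**Working it through.** **The plan's own figures.** Protocol section 14.4 and SAP section 1.4 take 10 µg/L (the same as 10 ng/ml) as the relevant change and 20 subjects as the sample size. With a pre-treatment SD of 4, a post-treatment SD of 12 and no correlation (which the plan's first scenario also implies), the SD of the difference is √(16 + 144) = 12.65. A two-sided paired t test at 0.05 with 90% power (carried over from the first scenario) then needs 19 subjects, and 20 give 91.8%. The stated number is reproduced within one subject, so the sample size is not in dispute. The 10 serves below as the yardstick.

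**Inputs from the protocol.**
- Oral response, section 5.1: "a single oral dose of 45,000 IU dissolved in alcohol generally produced a rise in serum vitamin D of about 10 ng/ml". A second such dose added about another 10, which fits a roughly linear response over that range.
- Oral response, section 5.2.2: about 10 ng/ml per 50,000 IU.
- Speed, section 5.1: more than 60% of the rise occurs within 7 days.
- Common oral supplement sizes, section 5.1: 1,000 to 2,000 IU.

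**Assumptions, not in the documents.** Some subjects start daily use at these sizes on Day 0. The response to daily dosing is proportional to the cumulative dose. Between 10% and 30% of subjects react.

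**Step 1, cumulative intake by Day 21.** 21 × 1,000 = 21,000 IU; 21 × 2,000 = 42,000 IU.

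**Step 2, rise per reacting subject** = cumulative IU ÷ reference IU × 10.
- At 50,000 IU per 10 ng/ml: 4.2 to 8.4 ng/ml.
- At 45,000 IU per 10 ng/ml: 4.7 to 9.3 ng/ml.
- If only 60% of the rise has appeared by Day 21 (a rough discount, not a bound): 4.2 × 0.6 = 2.5 at the low end and 9.3 × 0.6 = 5.6 at the high end.

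The full range is therefore 2.5 to 9.3 ng/ml.

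**Step 3, shift in the mean** = share reacting × rise per reacting subject.

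| Assumed share | Subjects of 20 | Low (2.5) | High (9.3) |
|---|---|---|---|
| 10% | 2 | 0.3 | 0.9 |
| 20% | 4 | 0.5 | 1.9 |
| 30% | 6 | 0.8 | 2.8 |

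Against the target of 10 ng/ml this is about 3% to 28%. It would weigh more if the true gel effect is small. For the first three candidates, at 300,000 units in total, section 5.2.2 prints a mean change of 1.2, although its own row gives 12.1 − 10.2 = 1.9. The present study applies three times that total.

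All these figures concern supplements. The documents give no figure from which a dietary shift could be calculated.

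**The case against.** The strongest objection is that the content of the instructions is unknown. Section 9.2 has one phrase, and Appendix 1 is not in the text available. The handout might even tell subjects to keep their usual intake. The effect of moving it may also be small. Inclusion requires deficiency known before consent, and section 14.7 requires the study to be explained before enrolment, so subjects are aware of the problem whatever happens at baseline. The dietary route looks weak over 21 days: section 5.1 cites hospital students and doctors of whom 25% were deficient despite daily milk and a multivitamin. Finally, most of the possible harm would also be met by an ordinary on-study intake rule.

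All of this stands as a limit on size and certainty. It does not remove the gap: no passage restricts or records intake after Day 0, and the design has no other means of detecting a change.

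Two stronger readings are tempting and are not supported.
- **A reader might infer that the instruction would keep an ineffective gel from being stopped after the first 10 subjects.** The rule stops the study if changes are consistently below 10. The highest illustrated rise, 9.3, does not cross that threshold by itself. It would need a further contribution from the gel, assay variation or another source, and the plan does not define consistently. An effect on this rule is not shown.
- **A reader might infer a large false-positive rate.** The synopsis names a paired t test, but protocol section 14 and SAP section 1 exclude hypothesis testing and p-values. The point concerns bias in an estimated mean.

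**Conclusion.** The point holds in conditional form. An intake change prompted by the baseline instruction would be indistinguishable from gel effect and could bias the primary mean change upward. Whether it would occur, and in how many subjects, cannot be determined from the documents. The illustrated shift of 0.3 to 2.8 ng/ml rests on assumed reacting shares of 10 to 30%, new daily supplement use of 1,000 to 2,000 IU from Day 0, and proportional response; it is not an estimate. Diet alone would do less. The change is worth making because it is nearly free and the missing intake information cannot be recovered reliably after the study.

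**What to change.** In protocol section 9.2:
- On Day 0, ask subjects to keep their usual diet and any supplement use unchanged until the Day 21 draw, and to report any change at each visit. Add a line for this to Table 1 and the case report form. This request does most of the work, and the reports can be listed beside the primary result.
- Move general deficiency education that is not needed for consent or safety to after the Day 21 draw.
- Keep every other Day 0 instruction: gel application, skin self-assessment, tanning beds, arm covering, water submersion, and glucose monitoring in subjects with diabetes.

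The cost is a short protocol change, a revised handout and one question per visit. The downside is that general education comes three weeks later.
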